4.3.1. Primary Safety Observation

The following clinical outcomes will be collected for reporting. The initial reporting period will be all occurrences within 1 month (Day 0 - Day 30) from the index procedure. The outcome data will consist of:

- Aorta-Related Mortality
- Stroke
- Paraplegia
- Left Arm/Hand Ischemia

Primary Effectiveness Observation 4.3.2.

The primary effectiveness observation is treatment success (defined below) and will be captured within the initial reporting period of 1 month from the index procedure.

Treatment success is defined as:

Technical success, which is the successful delivery and deployment of the stent graft (deployment of the Valiant Mona LSA Thoracic Stent Graft System in the planned location with no unintentional coverage of other vessels, assessed intra-operatively, and the removal of the delivery system) and successful exclusion of the aneurysm/penetrating ulcer or primary entry tear while maintaining patency of the MSG and BSG at 30 day visit.

Additional Observations 4.3.3.

The following additional observations will be evaluated through the 30 day visit and at each follow up visit.

Major adverse events (MAEs) rates within 30 days of the initial or secondary procedures, including:

Form Medtronic

Revision [6.0]

Page 7 of 27

- All-Cause Mortality
- Myocardial Infarction
- Paraplegia
- Renal Failure
- Stroke
- Left Arm/Hand Ischemia
- Secondary endovascular procedures
- Secondary endovascular procedures for primary device failures (including Type I/III endoleaks, aneurysm expansion, aneurysm/aortic rupture, and BSG occlusion)
- Rupture
- **Endoleaks**
- Maximum aneurysm diameter change from baseline*
- Exclusion of aneurysm
- Exclusion of penetrating aortic ulcer (PAU)
- Stent graft patency
- Stent graft integrity
- Conversion to surgery
- Surgical revascularization of the LSA
- **Paraparesis**
- Adverse events including serious adverse events and device, procedure, and/or disease-related Adverse Events
- For CTBD, these additional observations will be evaluated:
 - Coverage of primary entry tear (exclusion of false lumen)
 - Extension of dissection (proximally or distally) with or without complications
 - Continuing or new false lumen (FL) perfusion
 - Primary intimal tear false lumen perfusion (PIT FLP)
 - Proximal aorta false lumen perfusion (PA FLP)
 - Distal aorta false lumen perfusion (DA FLP)
 - Proximal branch false lumen perfusion (PB FLP)
 - Distal branch false lumen perfusion (DB FLP)

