This process should be followed for each outcome, such that different images may be used for reporting on each outcome unless otherwise specified.

Table 2 shows which imaging outcomes are visible (marked with an "X") or invisible (not marked with an "X") using various imaging types. Evaluable images are images marked as "X" in the imaging matrix (Table 2) and a having response to "Was there evidence of <imaging outcome>?" of "Yes" or "No".

Revision [6.0]

Page 16 of 27

Images defined as 'Invisible' in the imaging matrix or any imaging assessment where the response to "Was there evidence of <imaging outcome>?" is "Not Applicable", "Not Evaluable", or blank/missing are not considered evaluable for imaging outcome analysis and are excluded.

Table 2. Imaging Matrix

Imaging Type	Migration	Endoleak	Device Integrity	Aneurysm Size Assessment	BSG/LSA Patency	MSG Patency
CTA or MR with Contrast	Х	Х	Х	Х	Х	Х
CTA or MR without Contrast	Х		Х	х	Х	Х
Chest Radiograph	Х		Х			
Doppler US					Х	

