7.9.2. Primary Effectiveness Observation

The primary effectiveness observation is Treatment Success that is defined as successful delivery and deployment of the stent graft (deployment of the Valiant Mona LSA Thoracic Stent Graft System in the planned location with no unintentional coverage of other vessels, assessed intra-operatively, and the removal of the delivery system) and successful exclusion of the aneurysm while maintaining patency of the MSG and BSG at the 30 day visit. Descriptive statistics (frequency and percentage) will be calculated for the primary effectiveness endpoint. A two-sided 95% confidence interval will also be calculated using the exact binomial method.

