7.9.3.5. Endoleaks

Type of endoleak includes Ia, Ib, Ic, type I combined, II, III, IV, and undetermined. The rate of these events will be reported for the 30-days visit, 6-month visit and at each annual follow-up and will be reported as the composite rate of endoleak requiring intervention or endoleak observed by imaging

VML_Eval Statistical Analysis Plan **Form** Medtronic Revision [6.0] Page 24 of 27

assessment. The endpoint will be analyzed using the core lab imaging assessment and the site reported imaging assessment, separately.

The endpoint will be reported descriptively with frequency counts and percentages for any endoleak as well as by type.

- The numerator will include all subjects having endoleak requiring intervention within the analysis time window or any endoleak reported on imaging assessment within the time window.
- The denominator will include all subjects having endoleak requiring intervention within the analysis time window or having evaluable imaging assessment within the time window.

For imaging assessment, any endoleak reported during the time window will be accounted for in analysis. The secondary procedure date will be used as the basis of determining if an endoleak requiring intervention occurred within the time window.

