- a. If at least one positive (event) imaging assessment is found for an event type (e.g., fracture) - select the earliest positive assessment and then apply the visit window rules: The event will be included in the rate calculation for the corresponding visit, and for any visit after this one, that patient will be excluded from both the numerator and denominator of the event rate calculation;
- b. If no positive imaging assessment is found, select the one using the 'latest evaluable image showing no event in the window rule';
- c. Steps a and b need to be repeated for each specific event, such that a different image may be used for reporting each event type.
- d. These observations will be assessed separately, for example, if a patient is determined to have fracture at 1-month, that patient will be excluded from fracture rate calculation for the visits after 1-month, but if no data support that the same patient has migration or kinking at 1-month, that patient will be included in the rate calculation at the later visit if the data are available until the relevant event(s) is/are determined.

Rate of Recurrent Imaging Observations

The following imaging assessments will be identified and reported by investigators per protocol definition; these events may appear or disappear through the imaging assessment from time to time:

Loss of stent graft patency

More detailed programming rules are described below:

- Slot all non-missing (evaluable) imaging assessments into the correspondent reporting
- b. If multiple imaging assessments are found within the same visit window:
 - i. If there is any positive finding for the event on evaluable images in the window, select the earliest image showing a positive finding e);
 - ii. If there is no positive finding for the event, select the latest evaluable image showing no event.

VML_Eval Statistical Analysis Plan **Form** Medtronic Revision [6.0] Page 26 of 27

Similar rules will be applied for the aortic artery measurement (such as diameter and length, etc.) during the follow-up visits.

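### Loss of stent graft patency is scored from Table 2 images only, so an occlusion found and reopened at a procedure can be missed, whereas a treated endoleak is counted

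*SAP*

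**What the plan says.** Loss of stent graft patency is the only event that SAP 7.9.3.6 treats as a recurrent imaging observation, that is, one that can come and go between images. Its programming rule starts from images: "Slot all non-missing (evaluable) imaging assessments into the correspondent reporting" (the line breaks off in the text available). With several images in a window, "If there is any positive finding for the event on evaluable images in the window, select the earliest image showing a positive finding". Failing that, "If there is no positive finding for the event, select the latest evaluable image showing no event".

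Section 7.2.3 defines evaluable. The image type must be marked for the outcome in Table 2, and the form must carry a Yes or No answer. All other images "are not considered evaluable for imaging outcome analysis and are excluded". Table 2 has four rows: CTA or MR with contrast, CTA or MR without contrast, chest radiograph, and Doppler ultrasound. BSG/LSA patency is marked for both CTA/MR rows and for Doppler. MSG patency is marked for the two CTA/MR rows only. Catheter angiography has no row.

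For endoleak, 7.9.3.5 takes a different route: "The numerator will include all subjects having endoleak requiring intervention within the analysis time window", or with an endoleak on imaging. The denominator is built the same way, and treated cases are dated by the secondary procedure.

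Section 4.3.3 lists secondary endovascular procedures for primary device failure, with reasons that include "aneurysm/aortic rupture, and BSG occlusion". The analysis list in 7.9.3.1 has secondary endovascular procedures and surgical revascularization of the LSA, without a breakdown by reason. Patency is also part of treatment success in 7.9.2, worded as "maintaining patency of the MSG and BSG at the 30 day visit".

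**The concern.** Treatment can remove an occlusion before any listed image records it. The SAP allows for this with endoleak but not with patency, although it describes patency loss as something that may disappear from one image to the next. Branch patency is a central performance measure for a device with a subclavian branch, and it is a component of the primary effectiveness observation. The study is descriptive, so the reported rate and its interval are the result. Section 4.2 adds that the data may support marketing applications. A rule that can only omit events makes the patency result look better than it was, and a reader of the patency table would have no sign of it.

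**Working it through.** The SAP states no patency rate, sample size calculation or power to reproduce. The check is to trace one case through the written rules and then size it.

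**Step 1: trace.** Assume a BSG occlusion found and reopened at catheter angiography on Day 20, and a CTA on Day 35 that shows flow. Both days lie in the 1-month imaging window of 15 to 122 days (Table 1).

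- The Day 20 angiogram is not a Table 2 image type, so it is not evaluable.
- The Day 35 CTA is evaluable and negative. It is the only evaluable image in the window, so it decides the result: no loss of patency. The choice of the latest negative image formally covers windows with several images. With several patent images it gives the same answer.
- Without the Day 35 CTA, the subject has no evaluable image and leaves numerator and denominator.
- An endoleak treated on Day 20, with the same Day 35 CTA, adds 1 to the endoleak numerator and is in its denominator.

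**Step 2: direction.** Let x of 44 subjects have an imaged loss.

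- If the missed subject has a patent image, the rate is x/44 instead of (x+1)/44.
- If the missed subject has no image, it is x/43 instead of (x+1)/44, which is lower for every x below 43.

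The omission cannot raise the reported loss rate.

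**Step 3: size.** Inputs: a maximum of 44 subjects (SAP section 6) and a two-sided 95% exact binomial interval. The SAP names that method for the primary observations and the 7.9.3.1 events, and the General Methodology section asks for 95% intervals on key endpoints. The number of missed cases, and 20 evaluable subjects for a late visit or a subset, are assumptions.

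The lower limit is the 0.025 quantile of Beta(x, n−x+1), and the upper limit is the 0.975 quantile of Beta(x+1, n−x). For x = 0 the lower limit is 0 and the upper limit is 1 − 0.025^(1/n). With n = 44 this gives 1 − 0.025^(1/44) = 8.0%.

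| Evaluable | Missed cases added | Loss of patency | Exact 95% CI |
|---|---|---|---|
| 44 | 0 | 0/44 = 0.0% | 0 to 8.0% |
| 44 | 1 | 1/44 = 2.3% | 0.1 to 12.0% |
| 44 | 2 | 2/44 = 4.5% | 0.6 to 15.5% |
| 20 | 0 | 0/20 = 0.0% | 0 to 16.8% |
| 20 | 1 | 1/20 = 5.0% | 0.1 to 24.9% |
| 20 | 2 | 2/20 = 10.0% | 1.2 to 31.7% |

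If the single missed subject has no other image in the window, the comparison is 0/43 = 0.0% (0 to 8.2%) against 1/44 = 2.3% (0.1 to 12.0%).

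**The case against.** The strongest reply is that the event is not hidden. A reader might infer that no rate in the plan captures a treated occlusion, and the documents do not support that. Section 7.9.3.1 gives subject-level rates with exact intervals for secondary endovascular procedures and for surgical LSA revascularization. An occlusion that caused arm or hand ischemia could also count as a major adverse event and, within 30 days, in the primary safety composite. Section 7.10 summarizes adverse events by relationship and lists device malfunctions and failures. All of this stands. None of these outputs is a patency rate, however, and the procedure rate does not say which procedures were for occlusion.

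The mechanism is also narrow. If any CTA or MR, or for the BSG a Doppler, in the window shows the occlusion before it is reopened, the worst-case rule counts it even when later images show flow. The documents give no figure for how often an occlusion would be found only at angiography.

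A third reply is that migration, kinking and loss of integrity are imaging-only too, so endoleak is the exception. That is true, but 7.9.3.6 describes those events as likely to stay visible on later images. Patency loss is described the other way, so it is closer to endoleak.

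A reader might also infer that the by-reason procedure observation was removed. It was not: 4.3.3 still lists it, and 7.9.4 calls for descriptive statistics on additional observations. What is missing is a line for it in 7.9.3.1.

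Finally, 7.9.3.6 refers to the protocol's definitions, and the protocol supplied has no readable body. A wider definition there cannot be ruled out.

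**Conclusion.** The point holds in a limited form. As the SAP is written, a BSG or MSG occlusion that is found and reopened at a procedure, and never seen on a Table 2 image marked for that outcome, is missing from the patency-loss rate. The error runs in one direction. One such case is 2.3 percentage points of 44 subjects and moves the upper 95% limit from 8.0% to 12.0%. Two cases are 4.5 points, with an upper limit of 15.5%. The event counts are assumed; the asymmetry with the endoleak rule is on the page.

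It is tempting to conclude that treatment success is overstated as well. The text does not establish this. It asks for patency at the 30 day visit, which a reopened graft can meet, and only a reading of patency as uninterrupted would turn such a case into a failure. What the plan lacks is a rule for an occlusion treated before that visit. No hypothesis test or decision rule is affected.

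**What to change.** - In 7.9.3.6, define loss of patency separately for the BSG and the MSG. The numerator is subjects with a secondary procedure or surgical LSA revascularization for occlusion in the window, or with a positive evaluable image. The denominator is those subjects plus all subjects with an evaluable image. Date treated cases by the procedure, as 7.9.3.5 does.
- In 7.9.3.1, add secondary endovascular procedures for primary device failure, by reason, so that the 4.3.3 observation has an analysis line.
- In 7.9.2, as a supplementary line only, report treatment success with an occlusion treated before the 30 day visit counted as failure.
- Check the change against the protocol's definition of loss of patency.

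If the sponsor prefers to keep the imaging rule, the minimum is to label the rate as patency on imaging and to report treated occlusions beside it.

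The cost is SAP wording and a merge with the Secondary Procedure, Conversion to Open Repair and Adverse Event forms, which 7.9.3.1 already draws on for contact dates. This assumes that the forms record the reason for a procedure, which the 4.3.3 observation needs in any case. The downside is that the reported patency rate may be slightly less favourable.

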7.9.4. Subset Analysis

Subset analyses of the primary safety and effectiveness observations will be created for the subjects enrolled with aneurysms, penetrating ulcers, or chronic Type B dissections. Descriptive statistics will be used to analyze the primary observations, additional observations, and periprocedural and discharge clinical utility measures.

7.10.Safety Evaluation

Any Adverse events (AEs or SAEs) other than MAEs will be summarized by relationship and time period. Relationship will be site-reported in 3 categories, device-related, procedure-related and aneurysmrelated. If an AE is in 2 or more categories, it will be included in both or all summaries. All SAEs will be summarized separately. All AEs will be coded according to the Medtronic Endovascular Dictionary.

The rate of any AE will be calculated for following time periods:

- 0-30 days
- 31-365 days
- 366-730 days
- 731-1095 days
- 1096 -1460 days
- 1461 1825 days

The event rate is determined by number of subjects who had the event during the time period divided by number of subjects at risk at the beginning of the time period, i.e. number of subjects who are still in the study at the beginning of the time period.

Unanticipated Serious Adverse Device Effects (USADEs), Unanticipated Adverse Device Effects (UADEs) and deaths will be provided in a listing. Device malfunctions and failures will be listed.

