7.9. Evaluation of Objectives

7.9.1. Primary Safety Observation

The primary safety observation of this study is a composite endpoint that consists of 1) Aneurysm Related Mortality, 2) Stroke, 3) Paraplegia, and 4) Left Arm/Hand Ischemia within 1 month (0-30 days) of index procedure. Descriptive statistics (frequency and percentage) will be calculated for the primary

safety endpoint and its component events. A two-sided 95% confidence interval for the primary safety endpoint and its component will also be calculated using the exact binomial method.

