7.9.3. Additional Observations

7.9.3.1. Major Adverse Events and Major Clinical Events

The following observations will be assessed through clinical follow-up (office visit or phone contact):

- Major adverse events (MAEs) rates within 30 days of the initial or secondary procedures, including:
 - All-Cause Mortality
 - Myocardial Infarction
 - Paraplegia
 - Renal Failure
 - Stroke
 - Left Arm/Hand Ischemia
- Secondary endovascular procedures
- Rupture
- Conversion to surgery
- Surgical revascularization of the LSA
- **Paraparesis**

[figure not shown]
The rate of the above events will be calculated on the subject level, and for different reporting time points, the correspondent cutoff days will be used as shown in Table 3.

For each visit (or reporting time point), the event rate will be calculated as the proportion of the number of subjects with a certain event term over the number of evaluable subjects. The evaluable subjects at each reporting time point include all subjects who are enrolled by the snapshot date and

- 1) Had a clinical or safety event (e.g. MAE) within (on or before) the Reporting cutoff Days, or
- 2) Had a follow-up or days to last contact at or after the lower limit of the Reporting Window,

Revision [6.0]

Page 19 of 27

[figure not shown]
3) The Withdrawal Consent Date /Recorded Lost-to-Follow-up Date at or after the lower limit of the Reporting Window

'Days to MAE' (date of earliest MAE – date of index procedure) and 'Days to Last Contact' (date of last contact – date of index procedure) are usually used for the determination of the eligibility of the 'evaluable subject'. The last contact date will be calculated based on the information gathered from all available dates during the follow-ups.

Similarly, 'Days to any AEs' and 'evaluability' of any AEs will be determined with the same principle as described above.

- 1. For death, Use the date of death from the CEC form, if it is not available then use Date of Death from study exit form.
- 2. For withdrew ("Subject withdrew consent to participate in the study" or " Physician's decision to protect the welfare of the subject") or "Subject enrolled but not implanted, completed 1 month follow-up", use Date of Exit from study exit form.
- 3. For patients who exited study for LTF, complete FU, or other reason, use last known date in the study from:
 - 1) Adverse Event Form
 - (i) Date event started
 - (ii) Date of resolution
 - 2) Secondary Procedure Form: Date of secondary procedure

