7.9.3.6. Technical Observations

A technical observation is defined as a defect, malfunction, or failure of the device. Also, this may pertain to the device or system not functioning according to its designed intent. These might include (but are not be limited to) stent fracture, migrations, and device access difficulties. Technical observations may or may not be related to an adverse event in a subject.

Technical observations that are not associated with any untoward medical occurrence in a subject will be reported on the Imaging Exam Forms, Index Endovascular Procedure Form or Secondary Procedure Form. Technical observations that result in an Adverse Event will be considered by definition as Adverse Device effects and must also be documented in an Adverse Event form.

Technical observations may be analyzed using site-reported imaging assessments or core lab reported imaging assessments, separately.

Rate of Non-recurrent Imaging Endpoints

The following imaging assessments will be identified and reported by investigators per protocol definition - once such an event is discovered through an imaging assessment, it will likely stay noticeable on the subsequent imaging assessments at all follow-ups:

- Stent graft migration
- Stent graft separation
- Stent graft kinking
- Stent graft twisting
- Loss of stent graft integrity

Revision [6.0]

Page 25 of 27

The rate of these events will be reported for the 30-day visit, 6-month visit and for each annual followup and calculated based on the number of subjects who had the event divided by the number of implanted subjects who are evaluated for that event at the time point. The imaging endpoint analysis time window will be used to determine that an image assessment belongs to a respective time point and the reporting details can be found in section 7.2.3.

Further, if such event is observed during a time window, it will most likely be observed on all the images thereafter (if the imaging visit is completed); hence only the first observed event will be used to calculate the event rate - once one such event is reported for a subject for a time point, that subject will be excluded from that event rate reporting for that same event term for any later time points.

More detailed programming rules are described below:

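### The visible SAP gives MAEs no device or procedure split: section 7.10 excludes them from the relationship summary, so related-AE rates omit any related event among the six MAE terms

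*SAP*

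**What the plan says.** Section 7.10 of the SAP opens with the rule at issue: "Any Adverse events (AEs or SAEs) other than MAEs will be summarized by relationship and time period". Relationship is site-reported as device-, procedure- or aneurysm-related, and "If an AE is in 2 or more categories, it will be included in both or all summaries". The rate in each period is the number of subjects with the event divided by the number still in the study when the period starts; the first period is Days 0 to 30. The same section adds that "All SAEs will be summarized separately", and for certain events it plans a listing: "Unanticipated Adverse Device Effects (UADEs) and deaths will be provided in a listing". Device malfunctions and failures are also listed.

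MAEs are handled in section 7.9.3.1. The six terms are all-cause mortality, myocardial infarction, paraplegia, renal failure, stroke and left arm/hand ischaemia, within 30 days of the initial or a secondary procedure. The rate is the "proportion of the number of subjects with a certain event term over the number of evaluable subjects", with an exact interval. Section 7.9.1 treats the primary safety composite in the same way: "A two-sided 95% confidence interval for the primary safety endpoint and its component will also be calculated".

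Section 4.3.3 lists among the additional observations "Adverse events including serious adverse events and device, procedure, and/or disease-related Adverse Events". It states no exclusion of MAEs.

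**The concern.** The stated purpose of the study is to assess the safety and effectiveness of a branched stent graft acutely and at 30 days, and section 4.2 says the data may support marketing applications. A reader will want to know how often early harm was attributed to the device or the procedure. As 7.10 is written, the rates that answer this leave out the most serious early events. Left arm/hand ischaemia is a telling example: it is both a primary safety component and an excluded MAE term, in a study of a left subclavian branch device.

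The MAE table cannot supply the missing information because no relationship split is stated for it. What is at stake is attribution, not the count of events.

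**Working it through.** The plan states no figure to reproduce, so the check is first a comparison of sections and then a sizing.

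**1. Where could the relationship of an MAE appear?**

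- 7.10, summary by relationship and period: split by device, procedure and aneurysm; MAEs excluded.
- 7.10, all-SAE summary: MAEs not excluded; no relationship split stated.
- 7.10, rate of any AE by period: MAEs not excluded in that sentence; no relationship split stated.
- 7.10, listings: deaths, unanticipated device effects, malfunctions and failures. These are listings, not rates.
- 7.9.3.1, MAE rates: all six terms, regardless of relationship.
- 7.9.1, primary safety: stroke, paraplegia and arm ischaemia regardless of relationship. Mortality is limited to aneurysm-related death, which is an attribution but not a device or procedure split.

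A non-fatal MAE that the site attributes to the device, and that is not classed as unanticipated, therefore has no stated output in the visible SAP that shows its relationship.

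**2. Effect on a rate.** For one relationship category and one period, let A be the subjects with a related non-MAE event, B the subjects with a related MAE, and N the subjects at risk at the start.

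- Rate as planned: |A| / N.
- Rate with MAEs included: |A or B| / N.
- Difference: (subjects in B but not in A) / N.

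A subject who has both kinds of related event is already in A and changes nothing.

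**3. Numbers.** N is up to 44 (section 6).

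- One such subject at N = 44: 1/44 = 0.0227, or 2.3 points.
- Because 44 is a maximum, one such subject at N = 18 + 5 = 23 (the subjects named in section 7.1.1.1, an assumption used only to show the range): 1/23 = 0.0435, or 4.3 points.
- If the tables are repeated by indication (section 7.9.4), one such subject in a group at the approximate 25% minimum of section 4.2, 0.25 × 44 = 11: 1/11 = 0.0909, or 9.1 points.
- Under the multi-category rule, one excluded event that is both device- and procedure-related can lower two rates.

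**4. Illustration with assumed counts at N = 44, exact 95% intervals.**

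| Subjects with related non-MAE event | Further subjects with only a related MAE | Rate as planned | Rate with MAEs |
|---|---|---|---|
| 0 | 2 | 0/44 = 0.0% (0 to 8.0%) | 2/44 = 4.5% (0.6 to 15.5%) |
| 5 | 2 | 5/44 = 11.4% (3.8 to 24.6%) | 7/44 = 15.9% (6.6 to 30.1%) |

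The counts are invented to show scale; the documents give none.

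**5. Periods affected.** The 30 days after the initial procedure coincide with the first period of 7.10, so every related event among the six terms in Days 0 to 30 is left out. MAEs are also defined around secondary procedures, so the same omission can arise in later periods.

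**The case against.** The strongest reply is that 7.10 declares its exclusion openly and gives MAEs a section of their own, where they are counted whatever their cause, by term and with exact intervals. Counting regardless of cause cannot understate harm from the device. Section 4.3.3 also lists MAEs and related adverse events as parallel items, so reporting the two groups apart is not clearly a contradiction. This stands in part: no event is lost, and the 7.10 rate is correct for what it says it measures. But nothing in 4.3.3 removes MAEs from the related events, and 7.10 is the only visible section that carries that item out.

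A second reply is that the answer may lie in material not available here. The supplied protocol has only page headers, part of the SAP was removed, section 7.2 promises subject listings of unspecified content, and section 7.2.4 refers to separate table shells. This stands as a limit. The point can be made only for the visible SAP.

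Three stronger readings are tempting and are not supported:

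- A reader might infer that every related MAE lowers a related-AE rate. The rate is per subject, so a subject who also has another related non-MAE event in the period is already counted.
- Section 7.9.3.6 says that "Technical observations that result in an Adverse Event will be considered by definition as Adverse Device effects". A reader might infer that a stroke following a malfunction is device-related by rule and then removed by 7.10. The SAP does not equate that classification with the site-reported categories of 7.10, and the malfunction itself would be listed.
- Table 3 reports MAEs to Day 1825 although they are defined within 30 days of a procedure. A reader might infer that a late stroke has no home. But a secondary procedure can occur at any time. On the plain reading a late stroke with no recent procedure is not an MAE, so it falls within the 7.10 summary and is split there.

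**Conclusion.** The point holds as a minor reporting correction. In the visible SAP, related events among the six MAE terms are omitted from the summary by relationship, and no other section states a device or procedure split for them. All MAEs are still counted. Deaths are least affected, since they are listed and aneurysm-related mortality has its own rate.

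The cost to a given rate is 2.3 points at N = 44 for each subject whose only related event in the period is an MAE, and more in a smaller group. No total can be given, because the number of such subjects is unknown. The study is descriptive, with no hypothesis tests, and neither primary observation changes. The conclusion assumes that the table shells and the protocol do not already supply the split.

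**What to change.** In 7.10, delete the words that exclude MAEs from the relationship summary. Alternatively, keep them and add one table of the MAE terms by the same three relationship categories, periods and denominators. In either case, add a footnote that MAEs also appear under 7.9.3.1. State as well whether the all-SAE summary includes MAEs and whether it is split by relationship.

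The cost is one wording change or one extra table. Relationship is already site-reported for adverse events, so no new data should be needed, and section 7.12 allows the change through an amended SAP. The drawbacks are that MAEs will be shown in two places, and that related-event rates may look slightly less favourable.
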